### **17.2.1 Overall Adverse Events**

Separate and combined safety analyses will be performed for the Safety population. All safety results will be presented separately for each treatment group. Safety endpoints will include adverse events (AEs), vital signs, ECGs, and laboratory parameters.

The principle of treatment emergence will be employed for the analysis of AE data. Treatment emergence is defined as any event that occurred following the initiation of therapy and was not present at baseline, or one which represents an exacerbation of a condition present prior to study entry (pre-existing).

Unresolved AE outcomes at the end of the study will be followed for an additional seven days or until resolution, whichever occurs earlier.

Adverse events will be classified by the Medical Dictionary for Regulatory Activities (MedDRA). For each study treatment, safety data will be collected and analyzed until treatment-emergent AEs are resolved. The type, incidence, timing (onset, duration), relationship, and severity of treatment-emergent AEs will be reported. Reasons for withdrawal due to AEs will also be reported.

Two-sided Fisher Exact tests will be performed to compare the two treatment groups with respect to incidence at the system order class level and for any preferred terms with >10 percent overall incidence.

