16.5.1 Overall Adverse Events

Separate and combined safety analyses will be performed for the Safety population. All safety results will be presented separately for each treatment group. Safety endpoints will include adverse events (AEs), vital signs, ECGs, and laboratory parameters.

The principle of treatment emergence will be employed for the analysis of AE data. Treatment emergence is defined as any event that occurred following the initiation of therapy and was not

present at baseline, or one which represents an exacerbation of a condition present prior to study entry (pre-existing).

Unresolved AE outcomes at the end of the study will be followed for an additional seven days or until resolution, whichever occurs earlier.

Adverse events will be classified by the Medical Dictionary for Regulatory Activities (MedDRA). For each study treatment, safety data will be collected and analyzed until treatment-emergent AEs are resolved. The type, incidence, timing (onset, duration), relationship, and severity of treatment-emergent AEs will be reported. Reasons for withdrawal due to AEs will also be reported.

Two-sided Fisher Exact tests will be performed to compare the two treatment groups with respect to incidence at the system order class level and for any preferred terms with >10 percent overall incidence.

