## 8. STUDY DESIGN

This is a group sequential, multicenter, randomized, double-blind, parallel-group, two-arm study comparing NRX-101 (n=37) to lurasidone (n=37) in a 1:1 ratio for the treatment of bipolar depression in participants with subacute levels of suicidal ideation, as reflected by the patient answering “yes” to item 3 and 4 on the C-SSRS within 4-weeks of screening, and do not require hospitalization.

Participants will be screened to ensure study eligibility prior to randomization on Day 1. Randomized participants will take either oral NRX-101 or lurasidone and placebo, in accordance with their treatment assignment, for 42 days. Participants will return to the investigational site on Day 70 for a follow-up visit (see Study Schema, Figure 3). During these visits, multiple psychometric scales will be completed, and participants will be assessed for safety, including the risk of increase in depression or suicidal ideation to the point where inpatient care or an alternative treatment is indicated.

**Figure 3** Study Schema

**Table 1** Schedule of Assessments

Visit Number	Screening		Treatment				Follow up 
	1	2	3	4	5	6	
Study Day	Day -10 to -1	Day 1  Baseline	Day 7	Day 14 	Day 28 	ET/Day 42 	Day 70
Informed Consent	X						
Eligibility Review	X	X					
Randomization		X					
Demographics	X						
Medical History	X						
Psychiatric History	X						
MINI	X						
MINI Severity/Disability		X				X	
Subject Eligibility	X	X					
Physical Exam 	X					X	
Vital Signs, Weight 	X	X		X	X	X	
ECG 	X	X				X	
Pregnancy Test (Urine dipstick)	X	X					
Drugs of Abuse Screen (Urine dipstick) 	X	X	X	X	X	X	
Fasting Chemistry, Hematology	X					X	
C-SSRS 	X	X	X	X	X	X	
MADRS	X	X	X	X	X	X	
CGI-SS	X	X	X	X	X	X	
CHRT-C, -SR	X		X	X	X	X	
BPRS psychosis subscale	X	X	X	X	X	X	
BARS 	X	X	X	X	X	X	
PRISE	X	X	X	X	X	X	
Adverse Events		X	X	X	X	X	X
Concomitant Medications	X	X	X	X	X	X	X
Adherence device training 		X					
Dispense investigational product and review adherence 			X	X	X		
Site monitoring of adherence 				X	X	X	

 Follow up visit will be a phone call; the study visit may occur within  $\pm$  7 days of the scheduled day (anchored to the Day 1 visit).

 Day 1 procedures need to meet eligibility criteria and will be performed prior to first dose.

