### 18.2 Power and Significance

These sample size calculations are based on the alternative hypothesis corresponding to a 0.66 effect size which corresponds to a mean 8.85-unit MADRS-10 advantage change from baseline for NRX-101 vs control. A total of 74 subjects are to be randomized 1:1 to support the final analysis. As summarized below in Table 2, there is 80% power to detect a 0.66 effect size; a 0.462 effect size would reach two-sided  $p=0.05$ . A 0.462 (moderate) effect size reflects a 50 percent drop (based on lurasidone published data) in mean change from baseline for lurasidone with an assumed standard deviation of 13.4; this approximately corresponds to a -16 mean CFB for NRX-101 and a -10 mean CFB for lurasidone.

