## 20.5 Safety Endpoints

Adverse events will be classified by MedDRA. For each study treatment, safety data will be collected and analyzed while on treatment or until treatment-emergent adverse events are resolved. The type, incidence, timing (onset, duration), relationship, and severity of AEs will be reported for treatment-emergent and SAEs. Reasons for withdrawal due to AEs will also be reported. Narratives will be written for every AE classified as serious or associated with attempted suicide or death.

Safety and tolerability will be assessed using two-sided Fisher Exact tests to compare overall adverse event incidence for NRX-101 vs. lurasidone. Mean changes from randomization baseline will be displayed for each serum chemistry and hematology parameter as well as the shift; unpaired t-tests will be used to compare treatments. In addition, paired t-tests will be performed for the changes from randomization baseline for each study treatment group.

C-SSRS will also be considered as a safety endpoint but will be analyzed as a McNemar paired comparison test within treatment groups and as a Jonchkeere-Terpstra test to compare treatment groups.

Vital signs and ECGs (means and mean changes from baseline will also be evaluated within treatment groups using paired t-tests and between study treatment groups using unpaired t-tests. Percent with abnormal vital signs, heart rate, QRS duration, PR interval, RR interval, QT, and QTcF will be reported. McNemar paired comparison tests will be performed within study treatment groups for the abnormal discordant percent while two-sided Fisher Exact tests will be performed to compare incidences between treatment groups.

Blood draws for chemistries and hematologies will be evaluated within and between study treatment groups. Abnormality rates will be presented relative to established site-specific normal ranges and whether or not the abnormality is clinically significant. McNemar paired comparison tests will be performed within study treatment groups for the abnormal percents while two-sided Fisher Exact tests will be performed to compare incidences between treatment groups.

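### The 10% filter on preferred-term tests uses overall incidence, so a 6-0 or 7-0 split against NRX-101 gets no preferred-term test (minor, cheap to fix)

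*SAP*

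**What the plan says.** SAP 17.2.1 states: "Two-sided Fisher Exact tests will be performed to compare the two treatment groups". The sentence goes on to name two levels, "with respect to incidence at the system order class level and for any preferred terms with >10 percent overall incidence". Protocol 16.5.1 has the same rule ("incidence at the system order class level and for any preferred terms with >10 percent overall incidence"). The class level, evidently system organ class, has no threshold; the preferred-term level has one. Neither document defines overall incidence. Both arms pooled is the natural reading, because the sentence has just named the two groups being compared, but it remains an inference.

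Two other provisions bear on the point. SAP 20.5 plans a comparison with no threshold: "Safety and tolerability will be assessed using two-sided Fisher Exact tests to compare overall adverse event incidence for NRX-101 vs. lurasidone" (likewise Protocol 16.8.9). SAP 17.2.1 also says: "All safety results will be presented separately for each treatment group".

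The design is "comparing NRX-101 (n=37) to lurasidone (n=37) in a 1:1 ratio" (SAP section 8).

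**The concern.** Protocol 10.3 (Tables 2 and 3) gives lurasidone to both arms and D-cycloserine (DCS) to one. A reaction caused by DCS alone would appear in the NRX-101 arm only. With 1:1 allocation its pooled incidence is then half its rate among the patients exposed to DCS. A pooled filter is therefore strictest on reactions to the component under evaluation, while a term spread evenly over the arms passes at half the per-arm excess.

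At stake is whether a one-sided preferred term receives a p-value in a table where more common terms have one. A reader may take the missing p-value as no signal.

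**Working it through.** **Inputs.**
- 37 per arm and 74 in total (SAP sections 8 and 18.2).
- Two-sided Fisher exact test (SAP 17.2.1) at the 5% level (SAP 19.3).
- Safety population of all subjects as treated (SAP section 15). Taking this as 37 + 37 assumes that everyone randomized is dosed.

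**The plan's own figure.** The documents do not say what the 10% threshold can detect. The figure behind 37 per arm does reproduce: a t-test with effect size 0.66, 37 per group and two-sided 5% has 79.98% power, against 80% stated.

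**Threshold.** Pooled: 10% of 74 = 7.4, so at least 8 patients are needed (8/74 = 10.8%). In one arm: 10% of 37 = 3.7, so at least 4 are needed (4/37 = 10.8%).

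**Fisher p for k v 0 with equal arms.** The two extreme tables are equally likely, so p = 2 × C(37,k) / C(74,k).
- k=6: 2 × 2,324,784 / 185,250,786 = 0.0251
- k=7: 2 × 10,295,472 / 1,799,579,064 = 0.0114

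| NRX-101 v lurasidone (of 37 each) | Pooled | Fisher p | Preferred-term test under the plan |
|---|---|---|---|
| 5 v 0 | 6.8% | 0.054 | no |
| 6 v 0 | 8.1% | 0.025 | no |
| 7 v 0 | 9.5% | 0.011 | no |
| 6 v 1 | 9.5% | 0.107 | no |
| 4 v 4 | 10.8% | 1.000 | yes |
| 7 v 1 | 10.8% | 0.056 | yes |
| 8 v 0 | 10.8% | 0.005 | yes |

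Listing every table with 7 or fewer events in total, only 6-0 and 7-0 (either direction) give p<0.05.

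**What the class-level test recovers.** Start from 7 v 0 and add the same number of other patients with an event in that class to each arm:

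| Class-level counts | Fisher p |
|---|---|
| 7 v 0 | 0.011 |
| 8 v 1 | 0.028 |
| 9 v 2 | 0.046 |
| 10 v 3 | 0.064 |
| 12 v 5 | 0.096 |

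The class test keeps p<0.05 with up to two such patients per arm and loses it at three.

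**How often the gap could arise.** Assume, for illustration, a zero background rate and a true NRX-101 rate of 15%. The binomial chance of exactly 6 or 7 cases in 37 is 31%; of 8 or more, 18%. At true rates of 12% and 20% the chance of 6 or 7 is 21% and 31%. A background rate above zero lowers these.

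**Sensitivity to arm sizes.** At 35 per arm, 7/70 is exactly 10.0%, which is not above 10%, so 7-0 is still untested (p=0.011). Below 70 treated, 7 events pass (7/69 = 10.1%). With 36 on NRX-101 and 38 on lurasidone, a 5-0 split against NRX-101 also reaches p<0.05 (p=0.023) and is also filtered out, so the list of two splits is specific to 37 v 37.

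**The case against.** A reader might infer that such an event is never compared between the arms. The documents do not support that. The sentence that sets the filter also requires class-level tests with no threshold, and the 7 patients count there; if theirs is the only term in its class, the class test returns the same p=0.011. They also count in the any-adverse-event test of SAP 20.5, and the incidence of the term is shown by arm, so anyone with the table can compute the missing p-value.

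A reader might also infer that the filter keeps only lurasidone events that the design balances. That does not hold either: SAP 7.4 hypothesizes less akathisia on NRX-101, and Protocol 10.3 lets lurasidone be titrated in each arm, so testing common lurasidone events is informative.

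Other safeguards exist. Serious events get narratives (SAP 20.5), the DSMB reviews reported adverse events (SAP 12.7), and BPRS, PRISE, BARS and C-SSRS are compared between groups without an incidence filter (SAP 17.2.2). No stopping rule or success criterion is tied to a preferred-term p-value. The gap is narrow: one lurasidone case turns 7-0 into 7-1, which is tested and gives p=0.056.

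All of this stands and limits the size of the point. It does not remove it. The class-level test is diluted by unrelated events in the same class, and the any-event test more so. The plan attaches tests to preferred terms, and its rule for choosing them admits 4-4 and omits 7-0.

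**Conclusion.** The point holds in a narrow form. On the pooled reading, with 37 treated per arm, a preferred term at 6-0 or 7-0 (p=0.025 and 0.011) gets no preferred-term test. It is reported by arm and enters only the class-level and any-event comparisons. No other split reaching p<0.05 is lost.

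This rests on three assumptions: that overall means both arms pooled, that all 74 randomized patients are treated, and that the treated arms are equal in size. It does not show that a harm of the added drug would go unseen. Severity is minor; the change is worth making because it is nearly free.

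**What to change.** In SAP 17.2.1 and Protocol 16.5.1, replace the preferred-term condition with: *>10 percent incidence in either treatment group*. This also settles the undefined word. The threshold becomes 4 of 37 in one arm, so 6-0 and 7-0 are both tested.

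No planned test is lost. Pooled incidence is a weighted average of the two arm incidences, so a term above 10% pooled is above 10% in at least one arm.

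The cost is a few more unadjusted, descriptive p-values and slightly more chance findings. Some added tests cannot reach 0.05 at 37 per arm (4-0 gives p=0.115, 5-0 gives p=0.054). Sample size, data collection and the efficacy type I error are unaffected. The edit should be made before database lock.

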### **17.2.2 Other Safety Measures**

The timing and incidence of adverse findings will be compiled following planned surveillance of all study participants by a designated safety monitor.

Vital signs and ECGs will also be evaluated within and between study treatment groups. The overall ECG interpretation will be reported as normal or abnormal; if abnormal, then the percent clinically significant will be reported.

While symptom improvement will be evaluated by assessing changes in the secondary outcome measures (CHRT, MADRS, and CGI-SS), safety measures in the C-SSRS, PRISE, BPRS, and BARS (including the global severity rating) will be evaluated within and between study treatment

groups. The timeframe is for both lifetime and the past six months for the baseline Screening scale and since the last visit for the Since Last Visit scale.

## 18. SAMPLE SIZE CALCULATIONS

### 18.1 Background

For DCS treatment group in major depressive disorder Heresco-Levy identified a 0.91 effect size for Hamilton-D Total and a 0.95 effect size for BDI-II ([Heresco-Levy, 2013](#)) and an effect size of >1 was seen in the phase 2 STABIL-B study with a similar effect size observed by Chen and Heresco Levy.

A more modest 0.66 effect size is targeted in the sample size calculations assuming a 1:1 allocation for a two-sided hypothesis test with 5% Type I error.

### 18.2 Power and Significance

These sample size calculations are based on the alternative hypothesis corresponding to a 0.66 effect size which corresponds to a mean 8.85-unit MADRS-10 advantage change from baseline for NRX-101 vs control. A total of 74 subjects are to be randomized 1:1 to support the final analysis. As summarized below in Table 2, there is 80% power to detect a 0.66 effect size; a 0.462 effect size would reach two-sided  $p=0.05$ . A 0.462 (moderate) effect size reflects a 50 percent drop (based on lurasidone published data) in mean change from baseline for lurasidone with an assumed standard deviation of 13.4; this approximately corresponds to a -16 mean CFB for NRX-101 and a -10 mean CFB for lurasidone.

**Table 2 MADRS-10 Change From Baseline Outcomes: T-tests**

	Power	Significance
Test significance level, <math>\alpha</math>	0.05	0.05
1 or 2 sided test	2	2
Effect size, <math>d =  m_1 - m_2  / s</math>	0.66	0.462
Power (%)	80	NA
N per group	37	37

### 18.3 Hierarchical Testing Strategy

The secondary efficacy hypotheses will also be evaluated using a hierarchical testing strategy where testing continues as long as two-sided  $p<0.05$  is reached. The first such hypothesis to be tested will be for primary endpoint MADRS change from baseline to endpoint, then change from baseline in CGI-SS, followed by time to treatment failure in the NRX-101 and lurasidone groups.

### 18.4 Interim Analyses

Two interim analyses are planned. The first interim analysis (IA) assessing safety will be conducted six weeks after the first 30-35 participants have been followed for 6 weeks and the

second IA assessing futility (primary efficacy endpoint) will be performed after the first 45-50 participants have been followed for 6 weeks.

Each interim analysis has a different objective with neither interim analysis spending any Type 1 error. The study will be stopped at the first interim analysis if Serious Adverse Events are deemed statistically significantly more common in the NRX-101 group compared to the lurasidone group in a manner deemed by the DMC to pose a potential danger to human subjects. The study will be stopped at the second IA for futility if the conditional power (CP) is less than 10%. In the event that the study is not stopped for either safety or futility, then enrollment will continue until a total of 74 subjects are randomized. This preserves two-sided  $p=0.05$  for the final analysis.

The unblinded Sponsor biostatistician will perform the interim analyses for the Data Safety Monitoring Board (DSMB). The blinded Sponsor biostatistician will then adjudicate cases with respect to intercurrent events which impact analysis inclusion.

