16.6.3 Interim Analyses

Two interim analyses are planned. The first interim analysis (IA) assessing safety will be conducted six weeks after the first 30-35 participants have been followed for 6 weeks and the second IA assessing futility (primary efficacy endpoint) will be performed after the first 45-50 participants have been followed for 6 weeks.

Each interim analysis has a different objective with neither interim analysis spending any Type 1 error. The study will be stopped at the first interim analysis if Serious Adverse Events are deemed statistically significantly more common in the NRX-101 group compared to the lurasidone group in a manner deemed by the DMC to pose a potential danger to human subjects. The study will be stopped at the second IA for futility if the conditional power (CP) is less than 10%. In the event that the study is not stopped for either safety or futility, then enrollment will continue until a total of 74 subjects are randomized. This preserves two-sided p=0.05 for the final analysis.

The unblinded Sponsor biostatistician will perform the interim analyses for the Data Safety Monitoring Board (DSMB). The blinded Sponsor biostatistician will then adjudicate cases with respect to intercurrent events which impact analysis inclusion.

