## **12.7 Study Monitoring by the Drug Safety Monitoring Board (DSMB)**

The study will be monitored for safety, futility, and efficacy by a DSMB. Interim analysis for safety will be conducted six weeks after the first 30-35 participants complete Day 42 based on reported Adverse Events and Serious Adverse Events. The study may be stopped for safety concerns. A second DSMB assessment for safety and futility will be conducted when 45-50 participants have reached Day 42.

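### Does listing efficacy in the DSMB's remit (SAP 12.7) undermine the claim in SAP 18.4 that no Type I error is spent at the interim looks?

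*SAP*

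**What the plan says.** SAP 12.7, repeated in protocol 15.7, describes the board's task: "The study will be monitored for safety, futility, and efficacy by a DSMB". It then sets out two reviews. The first is a safety review after 30-35 participants, based on adverse events and serious adverse events, with a general power to stop for safety concerns. The second is described as follows: "A second DSMB assessment for safety and futility will be conducted when 45-50 participants have reached Day 42".

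SAP 18.4, repeated in protocol 16.6.3 and both Synopses, gives the stopping rules. The first look stops the trial if serious adverse events are statistically significantly more common on NRX-101 and the DMC judges this a danger. At the second look, "second IA assessing futility (primary efficacy endpoint) will be performed" after 45-50 participants, and the trial stops if conditional power is below 10%. The section says "Each interim analysis has a different objective with neither interim analysis spending any Type 1 error" and then "In the event that the study is not stopped for either safety or futility, then enrollment will continue until a total of 74". It concludes: "This preserves two-sided p=0.05 for the final analysis".

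SAP 8 labels the design: "This is a group sequential, multicenter, randomized, double-blind, parallel-group, two-arm study". SAP 12.7 and 18.4 do not refer to each other.

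**The concern.** The second look is an unblinded comparison on the primary endpoint, so the efficacy result exists at the moment when 12.7 gives the board an efficacy remit. If the board could stop for benefit there, a final test at the full two-sided 5% would no longer control the Type I error, and the closing statement of 18.4 would be wrong. The group-sequential label in SAP 8 could encourage that reading.

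There is a similar worry about safety. Someone reading 18.4 alone might take the significance rule for serious adverse events as the only route to a safety stop, and might think that the second look has no safety purpose. The test and level for that comparison are not named in 18.4.

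**Working it through.** **1. The plan's own figure.** SAP 18.2 gives a difference of 8.85, SD 13.4 (so d = 8.85/13.4 = 0.660), 37 per arm and two-sided α = 0.05. With a t-test on 2×37 − 2 = 72 degrees of freedom:

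- noncentrality = 0.66 × √(37/2) = 2.84, giving power 79.98% (stated: 80%);
- smallest significant d = t(0.975; 72) × √(2/37) = 1.993 × 0.2325 = 0.463 (stated: 0.462).

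Both reproduce. The sample size is that of one final test with the whole 5%, with nothing set aside for an interim efficacy test.

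**2. The sections side by side.**

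| | SAP 12.7 / protocol 15.7 | SAP 18.4 / protocol 16.6.3 / Synopses |
|---|---|---|
| First look | safety; AEs and SAEs; may stop for safety concerns | safety; stop if SAE excess is significant and judged dangerous |
| Second look | safety and futility | futility; stop if conditional power < 10% |
| Efficacy look, boundary or stop | none; the word occurs only in the opening sentence | none; only safety and futility end the trial early |
| Type I error spent | not mentioned | none |

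The sections agree on the number of looks and the participant counts. They differ in one word about scope and in whether safety is mentioned at the second look.

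**3. Type I error of the plan as written.** The second-look fraction is t = 45/74 = 0.608 to 50/74 = 0.676. Interim and final statistics are bivariate normal with correlation √t = 0.780 to 0.822. The null can be rejected only at the end.

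- Futility rule not obeyed: P(|Z_final| > 1.96) = 0.05.
- Futility rule obeyed, conditional power under the current trend (assumed, since the SAP does not name a method): stop if Z_interim < √t × [1.96 − 1.282 × √(1 − t)], which is 0.903 at 45 and 1.011 at 50. Error in favour of NRX-101 is 0.0229 to 0.0232, against a nominal 0.025.
- Futility rule obeyed, conditional power under the design effect: 0.0249.

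In every case the two-sided error is at most 5%.

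**4. What an efficacy stop would do if there were one.** The boundary here is supposed; the documents give none.

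| Supposed interim efficacy stop | 45 of 74 | 50 of 74 |
|---|---|---|
| two-sided 5%, futility stop ignored | 0.0793 | 0.0766 |
| two-sided 5%, futility stop obeyed (current trend) | 0.0375 + 0.0250 = 0.0625 | 0.0365 + 0.0250 = 0.0615 |
| two-sided 0.001, futility stop ignored | 0.0501 | 0.0501 |
| none (the plan) | ≤ 0.05 | ≤ 0.05 |

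In the second row the two terms are the errors for and against NRX-101. The size of the problem depends on the boundary one chooses to imagine, so it does not describe this plan.

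**5. The safety rule.** Taking two-sided Fisher at 5% with 15 to 18 per arm, the chance that significance is reached at the first look is 8-22% for SAE risks of 20% against 5%, 15-28% for 30% against 10%, 27-49% for 30% against 5%, and 0.6-3.5% for 10% against 5%. The risks are assumed, as the documents give none. Such figures would matter if significance were the sole route to a stop. It is not: 18.4 says when the trial will be stopped, not that it may be stopped only then, and 12.7 separately allows a stop for safety concerns and puts safety in the second review.

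**The case for a change.** The strongest case for acting is that the text is inconsistent and cheap to correct. The clause in SAP 13 that lets the SAP prevail over the protocol does not help, because both sections are in the SAP. The comparative efficacy result will exist at the second look, and in a trial of people with suicidal ideation the interim section should not be readable as leaving safety out of the larger look.

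The inconsistency stands, and so does the missing cross-reference. The consequence does not follow. Monitoring is not stopping, and a futility assessment on the primary endpoint already obliges the board to look at efficacy data, which gives the word a harmless meaning. The group-sequential label also fits a design whose only formal boundary is for futility. On safety, the two sections can be followed together without conflict.

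The unnamed SAE test is a gap that the SAP's own conventions largely fill: Fisher's exact test for adverse-event incidence (17.2.1, 20.5) and two-sided 5% testing by default (19.3, labelled there for the final analysis). Because the rule also needs the board's judgement, no fixed error rate depends on it.

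Two neighbouring matters are separate. The first look comes 6 + 6 = 12 weeks after its last participant is randomized and the second 6 weeks after its own, so the order would reverse only if the intervening 10 to 20 participants (45 − 35 to 50 − 30) entered in under six weeks; the documents give no accrual rate. The two sentences in SAP 12.2.6.2 on whether every suicide attempt is a serious adverse event do need to be reconciled, but they are not part of the mismatch between 12.7 and 18.4.

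**Conclusion.** No change follows. The efficacy wording in SAP 12.7 and protocol 15.7 is a clerical slip. The stopping rules in SAP 18.4, protocol 16.6.3 and both Synopses are consistent with one another, provide no efficacy stop, and keep the two-sided error at or below 5%. Deleting the word or linking the sections would alter no analysis, sample size or conclusion. Safety review at the second look and the board's discretion at the first are already stated in 12.7.

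This rests on the board acting on the rules in 18.4 and on no efficacy boundary existing elsewhere. No DSMB charter is among the documents; one that contained such a boundary would reopen the question. The supposed-stop figures (6.2% to 7.9% with an unadjusted 5% interim test, 5.01% at 0.001) and the Fisher probabilities depend on assumptions from outside the plan and are not a measure of its error.
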